8.2.3 Additional statistical analysis of selected secondary efficacy variables

For the “change from Baseline in MASES index at Week 16 in the subgroup of study participants with enthesitis at Baseline”, and for the “enthesitis-free state at Week 16 based on the MASES Index in the subgroup of study participants with enthesitis at Baseline” secondary efficacy variables, additional statistical tests and calculation of inferential statistics will be performed. As these tests are not part of the multiplicity-controlled procedure, the associated p-values are considered nominal and are not controlled for multiplicity.

For the enthesitis-free state responder variable, the logistic regression model described in Section 8.1.2 will be used for analysis. The p-values will be based on the conditional logistic regression model to test general association. Missing values will be imputed using the NRI.

For the MASES continuous variable, the Hypothetical Estimand approach used for other continuous variables will be applied based on the ANCOVA model describe in Section 4.2.1.7 and Section 8.2.2.

The results of these inferential statistics will be presented in a single table summarizing the estimates (OR for the binary endpoint, LSM for the continuous endpoint) with their 95% CI and the associated p-values. The results will be pooled with the results obtained for selected other efficacy variables (see Section 8.3.3).

8.3 Analysis of other efficacy variables

The following sections provide the derivation of the other efficacy endpoints which have not been mentioned earlier in the SAP.

8.3.1 Derivation of other efficacy endpoints

8.3.1.1 Time to ASAS20/40 response

Time to a given response (ASAS20 or ASAS40) will be defined as the time in days from the start date of first treatment dose until the first date when the response (respectively ASAS20, or ASAS40) is achieved.

Missing ASAS response data will not be imputed. Instead, study participants with no observed response, will be censored at their last visit with ASAS40 response data.

As mentioned later in Section 8.3.2, the analysis will be performed on the Double-Blind Treatment Period. Study participants who discontinue IMP prior to achieving a response will be censored at the minimum date between the date of treatment discontinuation as defined in Section 3.4 and the Week 16 visit date. Study participants who reach the end of the Double-Blind Treatment Period visit (and are still on treatment) without achieving the given response will be censored at the date of the end of the Double-Blind Treatment Period visit (ie, Week 16 Visit date).

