Unless stated otherwise, statistical tests of efficacy variables will be performed 2-sided and p-values will be rounded to 4 decimal places. P-values less than 0.0001 will be presented as “<0.0001” and p-values greater than 0.9999 will be presented as “>0.9999.” Statistical comparison will be performed at the 0.05 level of significance.

The SAS® outputs supportive of any inferential statistics that are part of the hierarchical testing procedure (ie, all inferential statistics associated with the endpoints in figure 4.1) will be provided as a separate PDF document in addition to TFLs. These outputs will be included in the ‘Documentation of Statistical Methods’ section of the clinical study report.

Unless specified differently in the SAP, the order of treatment groups to be presented in tables from left to right will be:

- Placebo
- Bimekizumab 160mg Q4W

Selected tables may include columns for:

- all study participants, regardless of study treatment
- all study participants on bimekizumab, regardless of whether they shifted from placebo after the Double-Blind Treatment Period or not
- study participants randomized on placebo who shifted to bimekizumab after the Double-Blind Treatment Period

The abbreviation for bimekizumab is BKZ and will be used in tables and listings headers. In the TFLs study participants on bimekizumab 160mg will be displayed as “BKZ 160mg Q4W”.

All study participants dosed with bimekizumab will be summarized in some TFLs in a treatment column labeled as “BKZ 160mg Q4W Total”.

For all TFLs not dedicated to the Double-Blind treatment period only, the Placebo-randomized study participants who shifted to bimekizumab after the Double-Blind Treatment Period will be summarized in a treatment column labeled as “Placebo / BKZ 160mg Q4W”.

Per protocol,

- visit windows of ± 3 days are permissible for all visits through Week 16 (included). The visit window is relative to the Baseline Visit.
- visit windows of ± 4 days are permissible for all visits after Week 16,
- for the SFU Visit, the visit should occur no more than 3 days prior to the scheduled visit date and within 7 days after the scheduled visit date.

Only data collected at the scheduled visit will be included in the analysis. The only deviations may concern PK data, unscheduled vendor data collected with a few days of delay, and MRI data (see below).

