In addition, a line plot by treatment group will be produced for some of the endpoints in the sequential testing hierarchy, displaying the mean change from Baseline for the following variables based on results obtained using MI: ASDAS-CRP, BASDAI, BASFI, Total Spinal Pain, Nocturnal Spinal Pain, PCS SF-36 and ASQoL. The plot will also be produced for ASDAS-CRP.

All other continuous and categorical variables will be summarized using descriptive statistics for Baseline, absolute values and change from Baseline at each visit (except for hs-CRP endpoint for which ratio to Baseline will be displayed). For other continuous variables whose value at Week 16 is part of the hierarchical testing procedure, descriptive statistics will also be provided using OC analysis. Categorical variables will be furthermore described using OC analysis.

The analyses on time to ASAS20/40 response will be restricted to the Double-Blind Treatment Period. Each time to ASAS20/40 response will be estimated and presented using the Kaplan-Meier product-limit method for each treatment group. The median time to response, including the 2-sided 95% CI, will be calculated for each treatment group. The Greenwood estimator will be used to estimate the variance of the survival. Comparisons of bimekizumab versus placebo will be analyzed using a log-rank test stratified by region and prior TNF α inhibitor exposure. The hazard ratio and 95% CI obtained from the Cox proportional hazards model as well as the p-value from the log-rank test will be displayed. The time points for calculating the number at risk is calculated in days but expressed in weeks, with each week corresponding to 7 days.

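### Censoring each Week 16 non-responder on their own visit date makes the end of the time-to-ASAS-response curve too high, and discontinuers have two possible censoring dates

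*SAP*

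**What the plan says.** Section 8.3.1.1 defines time to response as "the time in days from the start date of first treatment dose until the first date when the response" is achieved. It then gives three censoring rules:

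- **A.** Under the statement that missing ASAS data are not imputed, "study participants with no observed response, will be censored at their last visit with ASAS40 response data".
- **B.** Participants who stop IMP before responding "will be censored at the minimum date between the date of treatment discontinuation as defined in Section 3.4 and the Week 16 visit date". Section 3.4 sets the treatment discontinuation date in the double-blind period at treatment end date + 28 + 3 days.
- **C.** Participants still on treatment who reach the end of the double-blind period without response "will be censored at the date of the end of the Double-Blind Treatment Period visit (ie, Week 16 Visit date").

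Section 3.1 states that "visit windows of ± 3 days are permissible for all visits through Week 16 (included"), relative to Baseline. Section 8.3.2 applies Kaplan-Meier per arm on a scale of days, reports the median with its 95% CI, and compares arms by a log-rank test stratified by region and prior TNFα inhibitor exposure. It displays "The hazard ratio and 95% CI obtained from the Cox proportional hazards model" beside that p-value, without naming strata for the Cox model.

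**The concern.** Every Week 16 outcome comes from one planned assessment, yet the outcomes enter the analysis on up to seven different days (109 to 115 days after Baseline). Under rule C a non-responder seen on day 109 is gone before a responder seen on day 115 is counted, so the last steps of the curve are divided by a shrinking risk set. The date of attendance alone causes this; no dropout is needed.

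The outputs at stake are the end of the curve and the median with its CI. Table 4-3 schedules these tables and graphs for the Week 24 interim analysis, which supports a marketing application. A median shown when fewer than half of an arm responded would mislead.

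Separately, a participant who stops IMP without response meets both rule A and rule B, with different dates and no order of precedence. Rule A also refers to ASAS40 data although the section covers ASAS20 as well.

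**Working it through.** **Figures in the plan.** The SAP gives no figure for this analysis. The planning rates used below were checked through the stated power: 40% versus 15% with 200 and 100 participants and a continuity-corrected chi-square gives 99.6%, in line with the >99% in Section 2.4.1.

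**Inputs from the SAP.** Visit window ±3 days (3.1); ASAS40 visits at Weeks 1, 2, 4, 8 and 12 (8.3.3) and Week 16; arms of 200 and 100; Week 16 planning rates of 40%/15% for ASAS40 and 70%/30% for ASAS20 (2.4.1, 2.4.2).

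**Assumed, because the SAP does not give them.** Spread of visit days; share of the arm first responding at Week 16; cumulative response at each visit; no dropout.

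**Closed form for the Week 16 window.** Let S12 be the proportion without response after Week 12, h the share of those who first respond at Week 16, m_d the visits on day d, and n_d the visits on day d or later. Then

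S(end) = S12 × ∏ (1 − h × m_d / n_d).

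Example: cumulative response 36% after Week 12 and 4% of the arm first responding at Week 16, so the true end is 40%. S12 = 0.64 and h = 0.04/0.64 = 0.0625. With visits uniform over seven days, m_d/n_d runs 1/7, 1/6, …, 1/2, 1. The product of (1 − 0.0625/k) for k = 7 down to 1 is 0.8478. S(end) = 0.64 × 0.8478 = 0.5426, so the curve ends at 45.7%, which is 5.7 points too high.

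Overshoot with uniform scatter, S12 from 0.9 down to 0.4:

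| First responding at Week 16 (% of arm) | Overshoot (points) |
|---|---|
| 2 | 2.9-3.1 |
| 3 | 4.2-4.5 |
| 4 | 5.4-5.9 |
| 5 | 6.4-7.3 |
| 6 | 7.4-8.6 |
| 8 | 9.0-11.0 |

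Visit days peaked on the nominal day give more: 6.1-8.2 points at 4% and 10.3-15.1 at 8%. If every visit falls on the nominal day the overshoot is 0.

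**Simulation.** The last column is the share of trials in which the curve reaches 50% although fewer than half the arm responded. Ranges span the scattered visit patterns.

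| Arm and endpoint, assumed true cumulative response (new at Week 16) | Mean end of curve | False median |
|---|---|---|
| Bimekizumab ASAS40, 40% (4%) | 46-48% | 20-32% |
| Bimekizumab ASAS40, 45% (4%) | 51-53% | 42-51% |
| Bimekizumab ASAS40, 45% (2%) | 48-49% | 24-28% |
| Placebo ASAS40, 15% (3%) | 19-21% | 0-3% |
| Placebo ASAS20, 30% (4%) | 36-38% | 4-11% |
| Bimekizumab ASAS20, 70% (4%) | 75-77% | 0 |

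Single trials vary widely: for bimekizumab ASAS40 at 40% with uniform scatter, the 5th to 95th percentile of the overshoot is 1.3 to 11.4 points.

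**Effect of a repair.** With true cumulative response of 45% (4% new, uniform scatter), the curve ends at 50.6% under the SAP rule. It ends at 44.9% with either a common censoring day (day 115) or nominal visit days. The chance of reporting any median falls from 56% to 8.5% with the common day. At day 108, before the window opens, the SAP curve reads 41.0%, equal to the assumed 41%. With placebo at 18%, the mean log-rank z is 4.52 under the SAP rule, 4.52 with the common day and 4.54 with nominal days.

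**Discontinuers.** Take a treatment end date of day 28 and no response. Rule B gives 28 + 31 = day 59. Rule A gives the last visit with ASAS40 data: day 28 or day 56, or day 112 if visits continue off drug. Someone who leaves the study before Week 16 has no Week 16 date for rule B's minimum.

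**The case against.** Actual assessment dates are a legitimate time scale, the artefact is confined to the last few days of the curve, and the treatment comparison barely moves. This is an exploratory endpoint outside the multiplicity-controlled procedure, and no primary or key secondary result uses the rule. All of that stands and limits the weight of the point. It does not rebut the mechanism.

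Four stronger readings are tempting, and the document does not support them:

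- **A fixed overshoot, such as 5 to 8 points.** That range fits roughly 4-6% first responding at Week 16 with uniform scatter. The SAP states neither input.
- **A conflict between the curve's end and the Week 16 responder rate.** The curve estimates cumulative first response and censors discontinuers. The Week 16 analysis counts response at Week 16 with non-responder imputation. Some gap is legitimate, so the bias must be measured against cumulative response. If that truly exceeds 50%, the median is genuine.
- **An unstratified Cox model.** Section 8.3.2 is silent on strata; it does not say there are none.
- **Irreconcilable discontinuer rules.** Rule A can be read as general, with B and C as specific exceptions, and the Section 3.4 date is the SAP's common definition of discontinuation. That reading is reasonable, but the text does not state it, and two programmers could derive different dates.

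**Conclusion.** Followed as written, Section 8.3.1.1 biases the end of the Kaplan-Meier curve upward whenever Week 16 visit dates vary and some participants first respond at that visit. The plausible size is about 3 to 11 points (uniform scatter, 2-8% first responding at Week 16), up to about 15 with peaked scatter, and 0 without scatter. All of these rest on assumed inputs.

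A false median is a practical risk mainly for bimekizumab ASAS40: roughly 20-50% of trials if true cumulative response is 40-45%, itself an assumption. It is rare for placebo ASAS40 and does not arise for bimekizumab ASAS20 near 70%. The earlier curve and the log-rank test are essentially unaffected.

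The unclear precedence for discontinuers is a separate defect of wording. Its numerical effect is not quantified here because the SAP gives no dropout rate. The correction is worth making before the analysis, but it does not bear on the trial's main conclusions.

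**What to change.** In Section 8.3.1.1:

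1. Either censor all on-treatment Week 16 non-responders at one common administrative day at or after the end of the Week 16 window, or use planned visit times for both events and censoring. Either removes the overshoot; the first keeps actual days.
2. State one rule for participants who discontinue IMP without response: censor at the last visit with evaluable data for the ASAS response being analysed (ASAS20 or ASAS40), on or before the earlier of the treatment discontinuation date and Week 16.

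In Section 8.3.2, as a minor consistency point, state that the Cox model uses the same strata as the log-rank test.

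The cost is a few sentences and slight reprogramming, with no change to data collection. Planned visit times would create heavier ties, so tie handling should be stated if that option is chosen.

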8.3.1.2 ASDAS status

The ASDAS status endpoint is derived as follows based on ASDAS-CRP endpoint previously defined in Section 8.2.1.1:

- Inactive disease: when ASDAS-CRP <1.3
- Low disease activity: when ASDAS-CRP ≥ 1.3 to <2.1
- High disease activity: when ASDAS-CRP ≥ 2.1 to ≤ 3.5
- Very high disease activity: when ASDAS-CRP > 3.5

8.3.1.3 BASDAI50 response

A response variable called BASDAI50 is defined as an improvement of at least 50% in the BASDAI compared to Baseline. See Section 8.2.1.2 for details on the BASDAI endpoint.

8.3.1.4 Physician's Global Assessment of Disease Activity (PhGADA)

PhGADA is recorded by the investigator who will assess the overall status of the study participant with respect to their AS signs and symptoms and functional capacity using an NRS in which 0= “very good, asymptomatic and no limitations of normal activities” and 10= “very poor, very severe symptoms which are intolerable and inability to carry out normal activities”.

8.3.1.5 High-sensitivity C-Reactive Protein (hs-CRP)

In the summary tables presenting hs-CRP values, the observed values and ratio to Baseline values will be displayed.

Hs-CRP values which are below the lower limit of quantification (LLOQ) should be set to the midpoint between 0 and the LLOQ. The listing will show that the value was below the LLOQ. The LLOQ will be set according to data received by the laboratory vendor. Specifically, any numeric value preceded by “<” will be reset to a value equal to 0.5 * the numeric value following the “<” for each individual.

Particular attention will be given to extreme CRP values. Any CRP values of $\geq 500\text{mg/L}$ will be set to missing prior to performing the MI procedure; the subsequently imputed CRP value will be included in the summary tables. Listings will display the original result.

8.3.1.6 European QoL-5Dimensions 3-Level (EQ-5D-3L)

The EQ-5D-3L health questionnaire provides a descriptive profile and a single index value for health status. The instrument is composed of a 5-item health status measure (mobility, self-care, usual activities, pain/discomfort, anxiety/depression) and a visual analogue scale (VAS). Each of the 5 health states is divided into 3 levels (no problem, some or moderate problems, and extreme problems) and is scored as 1, 2, and 3, respectively. The 5 numerical responses are averaged to create the ‘utility scores’.

The change from Baseline in each of the 5 responses of the EQ-5D-3L will be analyzed categorically by visit. Additionally, the change from Baseline in the utility score will be summarized by visit using the numerical scores.

The EQ-5D VAS records the respondent’s self-rated health status on a vertical 20 cm visual analogue scale, graduated from 0 to 100 (0=worst imaginable health status, 100=best imaginable health status). The VAS will be evaluated by changes from Baseline and actual scores over time.

8.3.1.7 Short Form-36 (SF-36) Mental Component Summary (MCS) and the 8 domains scores (Physical Functioning, Role Physical, Bodily Pain, General Health, Vitality, Social Functioning, Role Emotional, and Mental Health)

As described in Section 8.2.1.6, the SF-36 is a survey that measures 8 health domains rated by the study participants over the past four weeks. MCS is based on the aggregate of these 8 health concepts and all these 8 health domain scales are used to score the MCS. The MCS and each domain scores are standardized with a mean of 50 and a standard deviation of 10 in the general US population, and a higher score indicates better health status.

Results for MCS as well as for each domain scores will be reported.

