2.2.1.3 Other efficacy variables

The following other efficacy variables will be assessed. These variables will be assessed at the time points defined in Table 5-2 of the protocol. All time points not specified in Section [2.2.1.1](#) or Section [2.2.1.2](#) of the SAP are considered exploratory.

- ASAS40 response
- Time to ASAS40 response
- ASAS20 response

- Time to ASAS20 response
- ASAS5/6 response
- ASAS-PR
- Change from Baseline in Ankylosing Spondylitis Disease Activity Score C-reactive protein (ASDAS-CRP)
- ASDAS status (eg, inactive disease [ID], low disease [LD], high disease [HD], and very high disease [vHD])
- ASDAS-MI
- Change from Baseline in BASDAI total score
- BASDAI50 response
- Change from Baseline in the average score of Questions 5 and 6 of the BASDAI concerning morning stiffness
- Change from Baseline in BASFI
- Change from baseline in the MASES index in the subgroup of study participants with enthesitis at Baseline
- Enthesitis-free state based on the MASES index in the subgroup of study participants with enthesitis at Baseline
- Change from Baseline in BASMI
- Change from Baseline in Physician's Global Assessment of Disease Activity (PhGADA)
- Change from Baseline in Patient's Global Assessment of Disease Activity (PGADA)
- Change from Baseline in total spinal pain score (based on Numeric Rating Scale)
- Change from Baseline in nocturnal spinal pain score (based on Numeric Rating Scale)
- Change from Baseline in high sensitivity C-reactive protein (hs-CRP)
- Responses to the European Quality of Life-5 Dimensions 3-Level (EQ-5D-3L) version
- Change from Baseline in EQ-5D-3L Visual Analog Scale (VAS) scores
- Change from Baseline in the EQ-5D-3L utility score
- Change from Baseline in the SF-36 PCS score
- Change from Baseline in the SF-36 Mental Component Summary (MCS) score
- Change from Baseline in Sleep Disturbance and Sleep Problems Index II score (Medical Outcomes Study [MOS 12-item] scale)
- Change from Baseline in Functional Assessment of Chronic Illness Therapy (FACIT) - Fatigue subscale score
- Change from Baseline in ASQoL total score

- Change from Baseline in Work Productivity and Activity Impairment Questionnaire-Specific Health Problem (WPAI-SHP)
- Change from Baseline in (44/44) tender joint count (TJC) and swollen joint count (SJC)

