^b Required only for by-visit summaries of variables whose value at Week 16 is part of the hierarchical testing procedure.

^c For variables with multiple categories, data will be summarized as observed with an additional missing row to capture missing data at a given visit.

^d MI will not be performed for the change from baseline in WPAI-SHP, change from baseline in EQ-5D-3L Utility Scores, change from Baseline in ASspiMRI-a (Berlin modification) score, or change from baseline in SPARCC score where only observed case analysis will be performed.

^e Performed only for components of the primary endpoint.

^f MI analysis will only be required for ASDAS status endpoint.

^g Last Observation Carried Forward (LOCF) will only be used for the secondary continuous endpoints in the hierarchy if the Reference-Based Multiple Imputation analyses do not converge.

In this section, two terms will be defined for binary endpoints:

- Binary endpoints derived based on one continuous measurement (eg, BASDAI50 at Week 16) will be called ‘non-composite binary endpoint’.
- Binary endpoints derived based on several continuous measurements (eg, ASAS40 at Week 16), will be called ‘composite binary endpoint’.

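### The EQ-5D-3L utility score in SAP Section 8.3.1.6 is an unweighted mean of level codes running from 1 (best) to 3 (worst), so the variable reported under that name is not a utility

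*SAP*

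**What the plan says.** Section 2.2.1.3 lists "Change from Baseline in the EQ-5D-3L utility score" as an other efficacy variable, separate from the item responses and the VAS.

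Section 8.3.1.6 introduces the questionnaire as one that "provides a descriptive profile and a single index value for health status". Each of the five dimensions (mobility, self-care, usual activities, pain/discomfort, anxiety/depression) has "3 levels (no problem, some or moderate problems, and extreme problems) and is scored as 1, 2, and 3, respectively". The derivation follows: "The 5 numerical responses are averaged to create the" utility scores. The next paragraph confirms that the analysis uses the same codes: "the change from Baseline in the utility score will be summarized by visit using the numerical scores". The VAS in that section is "graduated from 0 to 100 (0=worst imaginable health status, 100=best imaginable health status".

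The name recurs in footnote d of Table 4-1 (Section 4.2.1), where "change from baseline in EQ-5D-3L Utility Scores" is among the variables for which multiple imputation is not done, and in Section 8.3.2, which leaves the utility scores out of the hypothetical-estimand analysis. Neither place redefines the score. The SAP gives no value set, preference weights, anchoring or reverse scoring, and does not state the direction of this score.

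**The concern.** A utility, in the ordinary sense of the term, is a preference-weighted value of a health state, with full health at 1 and higher values better. The SAP's rule yields something else under that name. The level codes are ordinal severity labels. Averaging them gives every dimension equal weight and makes the step from 1 to 2 count the same as the step from 2 to 3. Because a higher code means a worse level, the scale also runs opposite to what the name implies.

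This is not a detail left open for the protocol or the programmers. The SAP states an explicit formula, and programming it faithfully produces the mislabelled quantity. At stake is whether results reported as EQ-5D-3L utility can be read as such.

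**Working it through.** The SAP states no numerical result for this score, so there is no figure to reproduce. The check applies the SAP's rule to the possible health states.

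**Inputs** (Section 8.3.1.6): five dimensions; codes 1, 2, 3 from no problem to extreme problems; score = (sum of the five codes) / 5.

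**Range and direction**
- No problem in any dimension: (1+1+1+1+1)/5 = 5/5 = 1.0.
- Extreme problems in all five: (3+3+3+3+3)/5 = 15/5 = 3.0.
- The best state therefore sits at the scale minimum, and every worse state scores above 1.
- A participant who goes from 2,2,2,2,2 to 1,1,1,1,1 changes by 1.0 − 2.0 = −1.0. Improvement is a fall on this score and a rise on the VAS.

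**Absence of weighting** (dimensions in the order listed in Section 8.3.1.6)
- Extreme pain, nothing else: (1+1+1+3+1)/5 = 7/5 = 1.4.
- Moderate pain and moderate usual-activity problems: (1+1+2+2+1)/5 = 7/5 = 1.4.
- Moderate pain and moderate anxiety/depression: (1+1+1+2+2)/5 = 7/5 = 1.4.

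**Full enumeration.** There are 3^5 = 243 states. Under the rule they collapse to 11 values, 1.0 to 3.0 in steps of 0.2. Fifteen states share the value 1.4, and 51 share 2.0. Only the number of severity steps counts, not where they fall.

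**What cannot be computed.** The SAP names no value set, so the size of the difference between this average and a true index, for any state or for the group means, cannot be derived from the document.

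**Reach.** Section 2.2.1.3 treats time points outside the primary and secondary lists as exploratory. Section 8.3.2 places the other efficacy endpoints outside the multiplicity-controlled procedure. Footnote d of Table 4-1 restricts the score to observed cases. Section 8.3.3 does not include it among the endpoints given nominal tests, and it is not among the line plots in Section 8.3.2.

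**The case against.** The strongest reply is that this is a naming fault with little consequence. The formula is open and reproducible. No planned inference depends on it. Section 8.3.2 has Baseline, absolute values and change all summarised, so a reader would see values between 1 and 3. Several instruments in this SAP improve downward (BASFI, BASDAI, ASQoL, BASMI), so running opposite to the VAS is not in itself an error. An average is also a single value, so the sentence about a single index value does not contradict the formula. All of this stands, and it limits the weight of the point. It does not rescue the definition, since the name is used as an endpoint name in Sections 2.2.1.3, 4.2.1 and 8.3.2 and nothing in the SAP makes the averaged score a utility.

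Three stronger readings are tempting and not supported:
- A reader might infer that a negative bimekizumab change would be taken as harm. The coding is published and absolute values are shown, so this is speculation. What can be said is that the name suggests one direction, the formula gives the other, and the SAP states neither.
- A reader might infer damage to a health-economic analysis. The objectives in Section 2.1 include no utility or cost-effectiveness aim, and the five responses are kept and analysed item by item, so an index could still be derived later.
- A reader might infer that every participant and visit is affected. Only participants with observed EQ-5D data at the scheduled visits contribute.

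It is also fair to say that no one value set is obviously right here: Table 3-1 lists 14 countries, and the SAP points to none.

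**Conclusion.** The point holds as a wrong derivation of one exploratory variable. The score defined in Section 8.3.1.6 is a mean level score from 1.0 (best) to 3.0 (worst), without preference weights, and reporting it as the EQ-5D-3L utility score would be wrong for participants with observed EQ-5D data at the scheduled visits. The direction and the ties follow from the SAP's own coding. That the score is not a utility rests on the general meaning of the term, not on an internal contradiction or a particular tariff.

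The impact is small: the type I error and the conclusions of the trial do not depend on this score. It should be corrected because the output would be mislabelled and the correction is cheap.

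**What to change.** Preferred: replace the averaging sentence in Section 8.3.1.6 with derivation of the index from the five-item health state, using a published EQ-5D-3L value set that the sponsor chooses and prespecifies in the SAP. With participants in 14 countries, the SAP should say whether one set is applied to all or country-specific sets are used. State that higher is better, and give a rule for missing items, as the SAP already does for BASFI, BASDAI and ASQoL.

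Minimum: keep the average, rename it EQ-5D-3L mean level score, state that it runs from 1 to 3 with higher worse, and stop calling it a utility in Sections 2.2.1.3, 4.2.1 (footnote d of Table 4-1), 8.3.1.6 and 8.3.2.

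The cost is SAP wording and, for the preferred option, a lookup table in programming. No new data are needed.
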